2 INTRODUCTION AND RATIONAL

2.1 Study Rationale

Fecal incontinence, also known as accidental bowel leakage, is a common condition that is an immense burden to older women, caregivers, and the health care system. Traditionally, fecal incontinence has been ascribed to obstetric neuromuscular injury, but preliminary results of a Penn led translational study in the Pelvic Floor Disorders Network show that gut microbiota may be a significant contributor (Arya et al., Neuro Uro, 2018). The overall goal of this study is to gather pilot data in order to conduct a future randomized controlled trial (RCT) for a novel treatment for fecal incontinence in older women utilizing fecal microbial transplantation (FMT). Our hypothesis is that infusion of intestinal microbiota from healthy donors to older women with fecal incontinence will increase microbial diversity, reduce symptom severity, and improve quality of life. We plan to conduct a single arm open label clinical trial of FMT for the treatment of fecal incontinence refractory to conservative management. We will measure the impact of FMT on change in symptom severity and quality of life and stool microbial diversity at 4 and 12 weeks after FMT.

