3 STUDY OBJECTIVES AND ENDPOINTS

OBJECTIVES	ENDPOINTS
Primary	
Determine if fecal microbial transplantation leads to clinical improvement in refractory fecal incontinence in older women.	Number of subjects that show significant improvement at 4 weeks after FMT, and will be maintained at 12 weeks, relative to baseline using the St. Mark's Vaizey score, a measure of fecal incontinence severity.
Primary Safety	
Determine the safety of FMT administration via naso-gastric tube in older women with FI.	Frequency of adverse events, serious adverse events, and adverse events of special interest (including allergic reaction and gastrointestinal symptoms).
Secondary	
Determine if FMT leads to improved quality of life for subjects.	Number of subjects that have an improved quality of life at 4 and 12 weeks, measured by the FIQL scale.
Determine if the effectiveness of microbial engraftment following fecal microbial transplantation is associated with the degree of clinical improvement.	Concentration of microbiota present at baseline vs. at week 4 and at 12 weeks (optional)in subjects that demonstrate a significant improvement at 4 weeks after FMT, relative to baseline using the St. Mark's Vaizey score.
Tertiary	
Determine whether the baseline microbiota of the subject affects engraftment in fecal microbial transplantation for fecal incontinence.	Concentration of microbiota at baseline vs. concentration of microbiota at 4 weeks and at 12 weeks (optional).

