9.2 Primary	
Determine if fecal microbial transplantation leads to clinical improvement in refractory fecal incontinence in older women.	Our working hypothesis is that the St. Mark's Vaizey score, a measure of fecal incontinence severity, will significantly improve at 4 weeks after FMT, and will be maintained at 12 weeks, relative to baseline. A secondary outcome will be quality of life at 4 and 12 weeks.
Primary Safety	
Determine the safety of FMT administration via NG tube in older women with FI.	Our hypothesis is that there will be low occurrence of serious adverse events following administration of FMT via NG tube.
Secondary	
Determine whether the effectiveness of microbial engraftment following fecal microbial transplantation is associated with the degree of clinical improvement.	Our working hypothesis is that more transplanted strains will be present at 4 weeks in subjects with a higher response score.
Tertiary	
Determine whether the baseline microbiota configuration affects engraftment in fecal microbial transplantation for fecal incontinence.	Our working hypothesis is that the transplant will be more effective in baseline samples with lower microbial diversity.

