9.4.2 Analysis of Stool Samples

Sequence reads from shotgun metagenomic sequencing will be subjected to quality control, taxonomic assignment, gene function analysis, and metagenomic assembly using the Sunbeam metagenomics pipeline, which was co-written by CHOP Microbiome Center researchers.

The FMT inoculum will be sequenced alongside fecal samples collected from subjects before and after the FMT procedure. DNA sequence reads from the inoculum will be assembled into contigs (overlapping DNA segments) using MEGAHIT (Li Bioinformatics, 2015). The metagenomic contig sequences represent segments of bacterial genomes from the microbiota. We will identify protein coding genes in the contig sequences, and use this gene set as unique identifiers for the genomes in the inoculum. Reads from patients before and after FMT will be aligned to the inoculum marker gene sequences. Gene sequences which are present in patients before the transplant will be removed from the set of inoculum marker genes. The percentage of total non-human reads aligning to the inoculum marker gene set will be used as a measure of bacterial engraftment following FMT.

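### The tertiary endpoint cannot answer the tertiary question (does baseline microbiota, in particular lower diversity, affect engraftment), and the diversity change promised in Section 2.1 has no endpoint or analysis

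*Combined protocol and SAP*

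**What the plan says.** **Diversity as an outcome.** Section 2.1 hypothesises that FMT "will increase microbial diversity, reduce symptom severity, and improve quality of life", and says the trial will measure the effect on "symptom severity and quality of life and stool microbial diversity at 4 and 12 weeks after FMT".

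**Diversity as a predictor.** The tertiary objective in Section 3 is to "Determine whether the baseline microbiota of the subject affects engraftment in fecal microbial transplantation for fecal incontinence". The tertiary row of the hypothesis table in Section 9 (under heading 9.2) predicts that "the transplant will be more effective in baseline samples with lower microbial diversity". The synopsis gives the same hypothesis but lists it among the secondary endpoints.

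**The endpoint.** For that objective Section 3 gives "Concentration of microbiota at baseline vs. concentration of microbiota at 4 weeks and at 12 weeks (optional" in brackets for the last visit. The secondary microbiome endpoint is also a concentration at baseline against later visits, restricted to women who improve.

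**The analysis.** Section 9.4.2 plans shotgun sequencing, taxonomic assignment, gene function analysis and assembly, and defines one summary measure: "The percentage of total non-human reads aligning to the inoculum marker gene set will be used as a measure of bacterial engraftment following FMT". Before that step, inoculum genes already found in patients before the transplant are dropped from the marker set. The only named test, the Friedman test in Section 9.4.1, is for symptom and quality-of-life scores. The detectable difference in Section 9.3 concerns engraftment by responder status.

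**The concern.** An objective of the form *does X at baseline affect Y* needs an analysis that relates X to Y across women. The tertiary endpoint compares one quantity with itself over time. It names neither the predictor in the hypothesis (diversity) nor the outcome in the objective (engraftment), so no result for it, however clear, would bear on the question. The quantity named is not one the laboratory plan yields either: a percentage of reads is relative, and no absolute quantification is described.

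The diversity change in Section 2.1 has a stated intent and visits, but no index, endpoint or analysis.

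What is at stake is the credibility of two exploratory answers from 15 women. If the index, read depth, visit and method are chosen after the data are seen, the result will be hard to defend as pilot evidence for the later randomised trial.

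**Working it through.** **1. Question against endpoint**

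| Question | Where stated | Needed | Planned |
|---|---|---|---|
| Does FMT raise diversity? | 2.1 | Index; change from baseline | None |
| Does baseline microbiota (lower diversity) affect engraftment? | 3, 9 | Baseline feature related to week-4 engraftment | Before-after concentration |
| Is engraftment related to clinical improvement? | 3, 9 | Engraftment by response | Measure in 9.4.2, detectable difference in 9.3; the Section 3 endpoint is again a before-after concentration |

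**2. The plan's own figure.** Section 9.3 gives 1.59 SD at a response rate near 60%, that is 9 responders and 6 non-responders. Level, sidedness and power are not stated; I assume two-sided 5% and 80%. For a two-sample t-test with 13 degrees of freedom, the noncentrality is 1.59 × √(9 × 6 / 15) = 1.59 × 1.897 = 3.02, and the power is 79.6%. The figure reproduces (80% power at 1.60 SD). It covers the third row only.

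**3. What 15 women can show on diversity** (same assumed level and power; 1.960 + 0.842 = 2.802)

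- Pearson correlation, Fisher z, 15 pairs: tanh(2.802 / √12) = tanh(0.809) = 0.67.
- Rank correlation, variance factor 1.06, 15 pairs: tanh(2.802 × √(1.06 / 12)) = tanh(0.833) = 0.68.
- Rank correlation, 12 pairs (assumed, to show the effect of missing samples): tanh(2.802 × √(1.06 / 9)) = tanh(0.961) = 0.74.
- Mean change in diversity, paired t: 0.78 SD of the within-woman change with 15 women, 0.89 SD with 12.

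**4. Whether the read share can serve as the engraftment measure.** Section 9.4.2 does not say whether baseline genes are removed per woman or pooled. If per woman, a woman with a richer baseline keeps fewer marker genes, so fewer reads can align to them even when true take is the same.

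To size this I simulated 15 women with true take independent of baseline. All inputs are assumptions: the share of inoculum genes already present at baseline is uniform over a range and stands in for diversity; take has mean 0.4; read share = take × (1 − share already present). False support means p < 0.05 in the predicted direction; the correct rate is 2.5%.

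| Already present | SD of take | Mean Spearman, read share | False support |
|---|---|---|---|
| 20–60% | 0.1 | about −0.57 | about 67% |
| 20–60% | 0.2 | about −0.32 | about 23% |
| 30–50% | 0.2 | about −0.18 | about 10% |

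When engraftment is instead the fraction of each woman's retained marker genes that is detected, the correlation centres on zero and false support is about 2.5% in all three cases. Letting overlap stand in fully for diversity is unfavourable; a looser link between the two would shrink the artefact.

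**5. Whether a before-after contrast can be kept.** Marker genes are those not found before the transplant, so the baseline read share is near zero by construction. Putting the read share into the existing Section 3 wording would compare almost nothing with something.

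**The case against.** The strongest reply is that this is missing detail, not a missing answer. Section 2.1 commits to measuring diversity, and taxonomic assignment of stool before and after FMT is all that an index needs. That stands: the questions are unanswered by the plan as written, not unanswerable. It does not rescue the tertiary endpoint, which is the wrong kind of comparison and not merely an unspecified one.

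The second reply is that this is a tertiary question in an uncontrolled pilot of 15. That also stands, and it limits the weight of the point. It is no reason to leave the endpoint mismatched when the data will already exist.

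Some stronger readings are tempting, but the documents do not support them:

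- *That diversity is the trial's mechanism.* Section 2.2 gives dysbiosis and butyrate pathways. Diversity is one of three changes hypothesised in Section 2.1, and the tertiary objective speaks of baseline microbiota more broadly.
- *That the trial would show only a before-after difference in composition.* Section 9.4.2 also yields engraftment, and Section 9.3 considers it by responder status.
- *That the later trial's population depends on this result.* No section says baseline diversity will be used to select women.
- *That correlating diversity with the read share is enough.* Step 4 of the working shows that it could confirm the hypothesis falsely.

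**Conclusion.** The point holds as a mismatch between objective and endpoint. The tertiary endpoint cannot address the tertiary objective or its hypothesis, the diversity change in Section 2.1 has no endpoint or analysis, and concentration is not what Section 9.4.2 measures. The change should be made, but it is not critical: the St. Mark's result and the safety summary do not depend on it.

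Even when repaired, the analysis will be imprecise. About |rho| = 0.68 is detectable with 15 complete pairs and about 0.74 with 12, under the assumed two-sided 5% and 80% power. The size of the built-in association (mean Spearman about −0.18 to −0.57) rests on illustrative inputs and on removal being per woman, which the protocol leaves open.

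**What to change.** Amend Sections 3 and 9.4.2, using only the sequencing already planned:

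1. Name one diversity index (Shannon would be one choice), computed at a common read depth. Report its change from baseline to week 4. Report week 12 descriptively in the samples available, because that stool is optional.
2. Replace the tertiary endpoint by the rank correlation, with 95% interval, between baseline diversity and week-4 engraftment. Present it as estimation, and state the detectable values (0.68 with 15 pairs, 0.74 with 12) with their assumptions.
3. State whether removal of baseline genes is per woman or pooled. For the correlation, measure engraftment as the fraction of each woman's retained inoculum marker genes detected at week 4, or otherwise adjust for the number retained.
4. In the Section 3 microbiome endpoints, replace concentration by the week-4 engraftment measure. For the secondary objective compare it by clinical response, not baseline against week 4.
5. Give the baseline-microbiota question the same rank in the synopsis as in Sections 3 and 9.

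The cost is SAP wording and a few lines of analysis. No new samples or assays are needed.

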4 STUDY PLAN

4.1 Study Design

Traditional treatments of fecal incontinence directed at obstetric neuromuscular injury, such as pelvic floor exercises and sphincteroplasty, have remarkably low efficacy in older women. The proposed study will provide critical feasibility and safety data for conducting a future randomized clinical trial of FMT versus placebo for the treatment of refractory fecal incontinence. We plan a single arm open label clinical trial of FMT for the treatment of refractory fecal incontinence. Older women with fecal incontinence who have failed prior treatment with diet modification and pelvic floor exercises will be invited to participate in the study. Penn Microbiome Therapy – 002 (PMT-002), which is derived from healthy screened donors will be delivered to the duodenum via a nasogastric tube. All subjects will complete validated questionnaires on fecal incontinence and contribute a stool sample for microbiota analysis at baseline and at 4 and 12 weeks after the FMT procedure.

4.2 Scientific Rationale for Study Design

For this first-of-its-kind pilot study, we plan to conduct a pre-post intervention study. No prior studies have assessed the impact of FMT on FI. Thus, we plan to assess the efficacy and safety of this treatment in this population prior to conducting larger placebo or alternate treatment comparison studies.

4.3 Justification for Dose and Route of Administration

There are several routes available for the administration of FMT. For this proof of concept study, FMT will be performed via duodenal infusion of donor stool rather than FMT capsules as a single study showed lower efficacy of capsules in women with irritable bowel syndrome (IBS). Our rationale for choosing FMT via duodenal infusion over colonoscopy is as follows: 1) Duodenal infusion FMT is an office-based procedure performed in an awake patient as compared to FMT via colonoscopy in the operating room under sedation, with a risk of bowel perforation and with much higher associated costs. 2) Duodenal infusion FMT is well tolerated by older adults (van Nood, NEJM, 2013; Pinn, Am J Gastro, 2014; Vrieze, Gastroenterol, 2012). 3) Several studies show that FMT via colonoscopy or duodenal infusion have equivalent efficacy (Ramai, Ann Gastro 2019). As described above, the dosing regimen for FMT in recurrent *Clostridium dificile* (R-CDI) will be used as there have been no studies on optimal dosing of PMT-002 in women with FI.

4.4 End of Study Definition

This clinical trial is considered completed (End of Study) when participants are no longer being examined or the last participant's last study visit has occurred (including long follow up visits or contacts).

A participant is considered to have completed the study if the subject has completed all phases of the study including the last visit or the last scheduled procedure shown in the Schedule of Activities (SoA), Section 2.3.

5 STUDY POPULATION

5.1 Inclusion Criteria

• Women \geq 50 years of age with self-reported fecal incontinence defined as:

- uncontrolled bothersome loss of liquid or solid fecal material that occurs at least weekly over the last 3 months **and**

- failure of response to conservative management using fiber, diet modification, supervised pelvic floor exercises

- Baseline St. Mark's score of ≥ 12
- Intolerance, unwillingness, or inadequate response to constipating medications
- Self-reported current negative colon cancer screening based on the 2016 US preventive Services Task Force recommendation (applies to participants age 50-75). N/A if participant is over 75
- Able and willing to sign the informed consent form and agree with study procedures

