1.2 Schema

Screening/Enrollment Week 12 (+/- 7 days) (80 days (+/- 7 days) Follow-Up: 30 & 60 minutes Treatment Visit 1 (within 30 days of screening *) Phone Contact # 1 (within 7 days of treatment) Week 4 (+/- 7 days) Phone Contact # 2 Study Visit 2 Study Visit 3 Procedures Informed Consent Х Demographics Х Medical History Х **Concomitant Medication** Х Х Х Х Х Х Review Abbreviated Physical Х X** X** X** Stool Collection PFIQ-7 Х Х Х Х Adaption Index Х Х Х **Dietary Screener** SF-12 Х Х Х PFDI-20 Х Х Х Pregnancy Test (women of Х Х Х Х childbearing potential) ABLe Questionnaire Х Х Х Radiologic/Imaging Х Assessment FIOL Х Х Х Bristol Stool Index Х Х Х Questionnaire St. Mark's Score Х* Х Х PMT Administration Х Vital Signs Review Х Х Symptom Review PGI-I Х Х Х PGSC Х Х Х **AE/SAE** Review Х Х Х Х Х Х Х Х Х Х Х Protocol Deviation Review Х

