1.3 Schedule of Activities (SoA)

Page 8 of 42

Procedures	< Screening/Enrollment	Treatment Visit 1 (within 30 days of screening *)	Follow-Up: 30 & 60 minutes	Phone Contact # 1 (within 7 days of treatment)	<pre>c Study Visit 2 Week 4 (+/- 7 days)</pre>	<pre>c Study Visit 3 Week 12 (+/- 7 days)</pre>	Phone Contact # 2 180 days (+/- 7 days)
Temperature Log	X				X	X	
Completion One Week BM Diary		X		X	X		
 * If time between screening and visit one is greater than 30 days, this test must be repeated prior to administration of FMT. ** Stool Collection will be performed by self-collection procedures and brought by the patient on day of study visit or mailed. 							

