8 STUDY ASSESSMENT AND PROCEDURES

8.1 Efficacy Assessments

8.1.1 Screening Visit

Potential candidates will be evaluated for eligibility per sections 6.1 and 6.2 and written informed consent will be obtained. Consented participants will be required to complete the following forms during their Baseline visit:

- Consent
- Eligibility Check List (includes St. Mark's Vaizey questionnaire)
- Pregnancy Test (if childbearing age)

If eligible, the following will be completed:

• Dietary Screener

• Questionnaires (Demographics, Medical History, SF-12, PFDI-20, ABLe Questionnaire, FIQL, Bristol Stool Index, PFIQ-7, Adaptation Index, PACSYM)

- Abbreviated Physical Exam
- Medication Log

Subjects will also be required to take the following home to complete prior to their treatment visit.

- One-week BM diary
- Stool Collection Kit (see stand-alone collection instructions)

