8.1.2 Visit 1: Treatment

At this visit, the study coordinator will collect the one-week BM diary and stool sample from the subject. The PI or another trained physician will meet with the patient. Vital signs will be done to document temperature, blood pressure, heart rate, and oxygen saturation. A nasogastric tube will be placed and secured. The subject will then be escorted to the radiology suite by the study coordinator. A chest x-ray will be performed to ensure adequate placement of the nasogastric tube. The PI or trained physician will confirm adequate placement of the tube with the attending radiologist. The subject will then be escorted back to the office suite by the study coordinator. The PI or trained physician will then administer the treatment. The PMT-002 product will be drawn into a syringe and the syringe will be connected to the nasogastric tube (NGT) and the product will be pushed into the tube until all of the FMT product is administered. The NGT will then be removed by the PI or trained physician. The subject will remain in the office for one hour following the administration of the PMT product.

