9.4 Statistical Analyses

9.4.1 General Approach

Data on safety outcomes will be summarized using descriptive statistics. Feasibility of conducting a clinical trial of FMT will be calculated by measuring the feasibility of conducting a clinical trial of FMT will be calculated by percentage of screened patients who enroll in the study (Number enrolled / Number screened x 100). Fecal incontinence severity symptom and quality of life (QOL) scores at baseline, 4 and 12 weeks after FMT treatment will be compared using Friedman test (repeated measures ANOVA for non-parametric data) Responder will be defined as 5 point or greater improvement in St. Mark's score from baseline to 4 weeks following FMT.

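### The screening St. Mark's score that must reach 12 appears also to be the analysis baseline, so regression to the mean is expected to favour FMT in this single-arm trial

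*Combined protocol and SAP*

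**What the plan says.** - **Entry.** Section 5.1 requires a "Baseline St. Mark's score of ≥ 12". Section 8.1.1 places the questionnaire at screening, within the "Eligibility Check List (includes St. Mark's Vaizey questionnaire"), and itself calls that visit the baseline visit: "Consented participants will be required to complete the following forms during their Baseline visit".
- **Outcome.** Section 3 counts women who improve significantly "relative to baseline using the St. Mark's Vaizey score, a measure of fecal incontinence severity". The synopsis (1.1) gives the primary endpoint as the change in the same score 4 weeks after FMT. Section 9.4.1 adds: "Responder will be defined as 5 point or greater improvement in St. Mark's score from baseline to 4 weeks following FMT". It compares baseline, week 4 and week 12 with a Friedman test and does not say which measurement is the baseline.
- **Schedule.** The "St. Mark's Score" row in section 1.2 has three marks, the first with an asterisk. The column positions are lost in the text available, but three marks fit screening, week 4 (8.1.4) and week 12 (8.1.5). Section 8.1.2 opens the treatment visit with "At this visit, the study coordinator will collect the one-week BM diary and stool sample from the subject" and goes on to vital signs, tube placement, X-ray and administration; it lists no St. Mark's score.
- **Repeat.** The footnote in section 1.3 reads: "If time between screening and visit one is greater than 30 days, this test must be repeated prior to administration of FMT". Nothing says whether the repeated score replaces the baseline or must again reach 12.
- **Design.** Single arm, open label, pre-post (4.1, 4.2), unblinded (6.3), 15 evaluable women (9.3).

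**The concern.** For a woman treated within 30 days of screening, the score that let her in is the only scheduled St. Mark's value before FMT. Any questionnaire score contains some error or short-term variation. Selecting on a score of at least 12 favours women whose error at screening was upwards, so their next score is expected to be lower with no treatment effect. On this scale, lower counts as improvement.

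A randomised comparison would cancel this shift. Here nothing does: there is no comparator, the Friedman test only compares time points within women, and no adjustment is planned. The shift goes straight into the mean change and the responder rate, and section 9.3 describes these as outcomes data for a future RCT.

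**Working it through.** **The plan's own figures.** The plan gives no figure for regression to the mean. Its two sample-size statements can be reproduced and are not affected. A two-sample t-test of 9 against 6 women, at two-sided 5% and 80% power (both assumed), detects 1.598 SD, against the stated 1.59. At a 60% response rate, 0.6745 × √(0.6 × 0.4 / 15) = 8.5 percentage points, consistent with the stated 10% as an interquartile statement.

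**Inputs.** From the documents: threshold 12, responder drop of 5 points, n = 15. Assumed, because the documents give none: mean μ of 10 to 16 and SD of 4 to 5 for the score among women screened, and test-retest reliability ρ of 0.6 to 0.9.

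**Formula.** With a stable true score, normal independent errors and no treatment effect,

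expected drop = (1 − ρ) × SD × φ(a) / (1 − Φ(a)), where a = (11.5 − μ) / SD

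(11.5 because scores are whole numbers).

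- μ = 12, SD = 4, ρ = 0.7: a = −0.125; 0.3 × 4 × 0.3958 / 0.5497 = 0.86 points.
- μ = 14, SD = 4, ρ = 0.7: a = −0.625; 0.3 × 4 × 0.3282 / 0.7340 = 0.54 points.
- Lowest, μ = 16, SD = 4, ρ = 0.9: 0.10 points.
- Highest, μ = 10, SD = 5, ρ = 0.6: a = 0.3; 0.4 × 5 × 0.3814 / 0.3821 = 2.00 points.

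**Simulation.** Whole-number scores, selection on screening ≥ 12, no treatment effect. The alternative baseline is a fresh pre-FMT score not used for selection.

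| SD 4, ρ 0.7 | Mean 12 | Mean 14 |
|---|---|---|
| Mean drop, screening baseline | 0.88 | 0.55 |
| Mean drop, fresh baseline | 0.0 | 0.0 |
| Responders, screening baseline | 11.1% (1.7 of 15) | 9.3% (1.4 of 15) |
| Responders, fresh baseline | 7.4% (1.1 of 15) | 7.4% (1.1 of 15) |
| 15-woman samples with a mean improvement, screening baseline | 86% | 75% |
| Same, fresh baseline | 48% | 49% |
| Friedman p < 0.05, screening baseline | about 15–16% | about 8–10% |
| Same, fresh baseline | about 5–6% | about 5–6% |

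Over the whole grid the spurious drop is about 0.1 to 2.0 points and the extra responders about 0 to 1.7 of 15. The largest excess is at mean 10, SD 5, ρ 0.6: 27.3% against 15.6%, and (0.273 − 0.156) × 15 = 1.8 from these rounded rates, 1.7 unrounded.

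**How much a Visit 1 baseline removes.** If screening and Visit 1 errors are independent, all of the shift. If they correlate at r, the fraction r remains: at r = 0.25, 0.5 and 0.75, 0.22, 0.43 and 0.65 of the 0.88 points.

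**Sampling error for comparison.** The exact 95% interval for 9 responders of 15 is 32% to 84%.

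**The case against.** The direction is standard; the dispute is over weight.

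- **The size is assumed.** This stands: the documents cannot show whether the shift is 0.1 or 2 points. The lower part of the range is also plausible. Section 5.5 has women approached after clinical confirmation of likely eligibility, and section 5.1 requires three months of at least weekly loss and failed conservative treatment. Both suggest a screened population well above 12. At means of 14 to 16 the grid gives about 0.1 to 1.0 points and at most about 0.7 extra responders. Section 5.4 also bars rescreening, so nobody gets repeated attempts at the threshold. These features limit the bias; they do not remove error from the qualifying score.
- **The effect on the responder count is small.** This stands too. Regression alone would almost never produce 9 responders of 15: under 1% of trials even in the extreme setting. But the mean change and the Friedman test are more sensitive, and unlike sampling error this error has a preferred direction.
- **Visit 1 may include the score.** The visit narratives are not exhaustive: 8.1.4 and 8.1.5 omit the pregnancy test that 8.2 requires. The reading is therefore natural rather than certain, which is itself a reason to define baseline.
- **The 30-day repeat already helps.** Only for women whose treatment is delayed, and only if the repeat serves as baseline and is not held to 12 again. As written, different women could have different kinds of baseline.
- **It is a pilot, and a later controlled trial would correct the drift.** This lowers the stakes. Section 9.3 does not say the response rate will size that trial, but it does say the outcomes data are gathered in order to conduct it.

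**Conclusion.** The concern holds, on the natural reading that the qualifying score is the analysis baseline. With a stable condition and any measurement error, the expected bias is towards FMT, and the design has nothing to offset it. Its size rests wholly on assumed score properties and on a model that selects on the score alone: negligible at one end, and at the other 2 points against a 5-point responder threshold. In a single trial of 15 women the realised error can go either way and may be small beside sampling error. The change is still worth making, because it removes a one-directional error from the primary efficacy result at very little cost. Confidence is medium, because of the assumed inputs and the undefined baseline.

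**What to change.** 1. Use the screening St. Mark's score for eligibility only.
2. Give the questionnaire to every woman at Visit 1 before FMT, and add it to the schedule and to section 8.1.2.
3. In section 9.4.1, define the Visit 1 score as the baseline for the week 4 and week 12 comparisons and for the responder rule. Do not apply the 12-point threshold to it, or the selection effect returns.
4. State in the schedule footnote what the repeat after 30 days is for. If it is an eligibility check, record it separately from the Visit 1 baseline.
5. Report change from the screening score as a sensitivity analysis.
6. State the limits: this reduces regression to the mean due to selection, and removes only part of it if errors at the two visits are correlated. It does not remove chance responders (about 1.1 of 15 in the central case), open-label response or natural fluctuation.

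The cost is one short questionnaire at an existing visit for 15 women, plus edits to the schedule, its footnote, section 8.1.2 and section 9.4.1. The other questionnaires would keep their screening baseline unless they are moved as well. The reported improvement may look smaller.
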